**Less Than Highly Effective Contraceptive Methods That Are User Dependent**

*Failure rate of >1% per year when used consistently and correctly.*

- Male or female condom with or without spermicide. Male and female condoms cannot be used simultaneously
- Diaphragm with spermicide
- Cervical cap with spermicide
- Vaginal Sponge with spermicide
- Progestogen-only oral hormonal contraception, where inhibition of ovulation is not the primary mechanism of action

**Unacceptable Methods of Contraception**

- Periodic abstinence (calendar, symptothermal, post-ovulation methods)
- Withdrawal (coitus interruptus).
- Spermicide only
- Lactation amenorrhea method (LAM)

**CONTRACEPTION GUIDANCE FOR MALE PARTICIPANTS WITH PARTNER(S) OF CHILD BEARING POTENTIAL.**

Male participants with female partners of childbearing potential are eligible to participate if they agree to the following during the treatment and until the end of relevant systemic exposure.

- Inform any and all partner(s) of their participation in a clinical drug study and the need to comply with contraception instructions as directed by the investigator.
- Male participants are required to use a condom for study duration and until the end of relevant systemic exposure defined as 7 months after the end of treatment in the male participant.
- Female partners of males participating in the study should consider use of effective methods of contraception until the end of relevant systemic exposure, defined as 5 months after the end of treatment in the male participant.
- Male participants with a pregnant or breastfeeding partner must agree to remain abstinent from penile vaginal intercourse or use a male condom during each episode of penile penetration during the treatment and until 5 months after the end of treatment.

- Refrain from donating sperm for the duration of the study treatment and for 7 months after the end of treatment.

## **COLLECTION OF PREGNANCY INFORMATION**

Guidance for collection of Pregnancy Information and outcome of pregnancy on the Pregnancy Surveillance Form is provided in [Section 9.2.5](#) and the Appendix for Adverse Events and Serious Adverse Events Definitions and procedures for Evaluating, Follow-up and Reporting

2 STUDY DESCRIPTION

2.1 Study Design

CA209923 is a Phase 1b, randomized, double-blind, multi-center study to evaluate the safety, tolerability, pharmacokinetics, and pharmacodynamics of a single dose of nivolumab in participants with severe sepsis or septic shock.

The study design schematic is presented in Figure 2.1-1.

Figure 2.1-1: Study Design Schematic

Screening	Baseline	Treatment	On-Treatment Assessments
Day -10 to -1	Day -1	Day 1	Day 1 to Day 90
Determine eligibility	Randomize eligible participants (1:1 ratio)	Single dose nivolumab 480 mg (n=15) OR	Hospital discharge may occur prior to Day 90

		Single dose nivolumab 960 mg (n=15)	
--	--	---	--

The total duration of study for each participant is approximately 100 days, comprised of a screening period of up to 10 days, plus a single dose on Day 1, followed by clinical study assessments up to Day 90. AEs and SAEs will be collected up to Day 90.

Physical examinations, vital sign measurements, 12-lead electrocardiograms (ECG), and clinical safety laboratory assessments will be performed at selected times throughout the study. Participants will be closely monitored for adverse events throughout the study. Serial blood samples for PK, RO, PD, biomarker, and immunogenicity analyses will be collected predose and at selected time points postdose. Up to approximately 452 mL of blood will be drawn from each participant during the study (within any 7 day interval, no more than 180 mL may be drawn). Clinical parameters of organ dysfunction will be assessed predose and at selected time points postdose during participants' index hospitalization.

2.2 Treatment Assignment

Subjects will be randomized to receive either single dose nivolumab 480mg or single dose nivolumab 960mg according to a randomization scheme generated by an Interactive Response Technology (IRT). Before the study is initiated, each user will receive log in information and directions on how to access the IRT.

During the screening visit, the investigative site will contact the Interactive Response Technology (IRT) system to assign the participant identification number. Once it is determined that the participant meets the eligibility criteria following the screening visit, the investigative site will call the IRT to randomize the participant into the open dose panel.

2.3 Blinding and Unblinding

Blinding of treatment assignment is critical to the integrity of this clinical study. However, in the event of a medical emergency or pregnancy in an individual participant in which knowledge of the investigational product is critical to the participant's management, the blind for that participant may be broken by the investigator. The participant's safety takes priority over any other considerations in determining if a treatment assignment should be unblinded.

Before breaking the blind of an individual participant's treatment, the investigator should determine that the unblinded information is necessary, i.e., that it will alter the participant's immediate management. In many cases, particularly when the emergency is clearly not related to the investigational product, the problem may be properly managed by assuming that the participant is receiving active product. It is highly desirable that the decision to unblind treatment assignment be discussed with the Medical Monitor, but the investigator always has ultimate authority for the decision to unblind. The Principal Investigator should only call in for emergency unblinding AFTER the decision to discontinue the participant has been made.

For this study, the method of unblinding for emergency purposes is IRT.

In cases of accidental unblinding, contact the Medical Monitor and ensure every attempt is made to preserve the blind.

Any request to unblind a participant for non-emergency purposes should be discussed with the Medical Monitor.

In case of an emergency, the investigator(s) has unrestricted access to randomization information via the Interactive Response Technology (IRT) and is capable of breaking the blind through the IRT system without prior approval from sponsor. Following the unblinding the Investigator shall notify the medical monitor and/or study director. For information on how to unblind in an emergency, consult the IRT manual.

Study participants and all clinical research site personnel, except the pharmacist, will be blinded. The pharmacist at the site and/or designee will be unblinded to the randomized treatment assignments in order to dispense treatment from bulk supplies, as needed.

Members of BMS Research and Development and their designees will be unblinded to study treatments to facilitate real-time analyses of PK, RO, and safety data in support of dose selection for future studies. No unblinded data will be communicated to Investigators or to other blinded clinical research site personnel. This unblinding is not expected to affect the integrity of the trial. PK and RO endpoints are objective assessments that should not be affected by unblinding, and BMS personnel will not communicate any trial results to the site to avoid any introduction of bias in safety assessments.

2.4 Protocol Amendments

This Statistical Analysis Plan (SAP) incorporates the Protocol Amendments below.

Document	Date of Issue	Summary of Change
Revised Protocol 01	03-Mar-2017	Incorporates Amendment 01
Amendment 01	03-Mar-2017	
The number of participants in the study was clarified as being “up to approximately 30” to reflect the fact that 30 participants is the maximum number planned. A key objective of this study is to characterize the pharmacokinetics (PK) of nivolumab in participants with sepsis, with the goal to obtain a PK profile from at least 6 subjects per dose level.
 
The body weight eligibility criteria was revised to (1) remove the word “ideal,” which was inadvertently included in the original protocol, and (2) align the upper limit of body weight with that studied in the nivolumab oncology development program.
 
In the original protocol, members of BMS Research and Development are blinded; in the amended protocol, they will be unblinded to study treatment in order to facilitate real-time analyses of PK, RO, and safety data in support of dose selection for future studies. The unblinded data and the corresponding analysis/report will be included in documents for communication with regulatory authorities. The investigators, all study personnel with the exception of

		
the pharmacist, and patients will remain blinded until the end of the study.
 
The discrepancy between textual description of the schedule for thyroid function testing in Section 9.4.4 and the tabular presentation in Table 2-2 was corrected.
 
A typographical error relating to time relative to dosing in hours at the Day 28 time point was corrected.
 
The potential interim analysis was removed because, in the amended protocol, the BMS team is fully unblinded thus the interim analysis becomes unnecessary.
 
The amendment applies to all subjects.

--	--	--

[figure not shown]
3 OBJECTIVES

3.1 Primary Objective

- To assess the safety and tolerability of a single dose of nivolumab 480 mg or 960 mg in participants with severe sepsis or septic shock
- To assess the pharmacokinetics of BMS-936558 in participants with severe sepsis or septic shock

3.2 Secondary Objective

- To assess receptor occupancy of nivolumab following single dose administration
- To assess the effect of a single dose of nivolumab on monocyte HLA-DR expression and absolute lymphocyte count
- To assess the immunogenicity of nivolumab following single dose administration

4 ENDPOINTS

4.1 Primary Endpoint

The primary objective (to assess the safety and tolerability) will be measured by the incidence rates of AEs, SAEs, AEs leading to discontinuation, immune-mediated AEs, and deaths. In addition, clinical laboratory tests, vital signs, and ECGs will be summarized.

The primary objective (to assess the pharmacokinetics of BMS-936558) will be measured by the following PK endpoints.

C_{\max}	Peak nivolumab serum concentration
C_{\min}	Trough nivolumab serum concentration
C_{avg}	Average nivolumab serum concentration
T_{\max}	Time of maximum observed concentration
CLT	Total clearance
V_d	Volume of distribution
$T_{1/2}$	Half-life
$AUC(0-T)$	Area under the serum concentration-time curve from time zero to time of last quantifiable concentration

4.2 Secondary Endpoints

- Receptor occupancy on T cells at baseline and after study treatment administration at planned sampling time points
- Baseline and post-dosing assessments of mHLA-DR expression on monocytes, and of absolute lymphocyte count
- Number and percentage of participants with detectable anti-nivolumab antibodies at baseline and following single dose administration of nivolumab and the relationship with other outcome measures

5 SAMPLE SIZE AND POWER

The number of participants is not based on statistical power consideration. Administration of nivolumab to up to approximately 15 participants in each arm provides an 80% probability of observing at least one occurrence of any adverse event that would occur with $\geq 10\%$ incidence in the population from which the sample is drawn.

The overall purpose of Study CA209923 is to evaluate the safety, tolerability, pharmacokinetics, and pharmacodynamics of two single doses of nivolumab in participants with severe sepsis or septic shock in order to inform feasibility and conduct of further studies of nivolumab in this population. Specifically, a key objective is to determine whether the exposures observed after a single dose of nivolumab in participants with severe sepsis or septic shock are comparable to the overall exposures observed at steady-state dosing with the nivolumab regimen approved in oncology indications. In order to achieve this goal, up to 15 subjects per dose level are estimated in order to obtain a PK profile from at least 6 subjects per dose level.

6 STUDY PERIODS, TREATMENT REGIMENS AND POPULATIONS FOR ANALYSES

6.1 Study Periods

This study consists two periods: pre-treatment and on-treatment.

The pre-treatment period begins with screening and extends until study drug administration on Day 1.

Measurements taken before Day 1 are considered pre-treatment for all data domains. In addition, measurements taken on Day 1 are considered pre-treatment for the following data domains: demography, SNP, medical history, physical measurements, inclusion/exclusion, and patient reported outcomes.

The on-treatment period begins with study drug administration on Day 1 and ends approximately 90 days after the dose date. It is expected that minimal drug exposure and undetectable drug levels will be present beyond 90 days post-dose.

Measurements taken after Day 1 through approximately Day 90 are considered on-treatment for all data domains. In addition, measurements taken on Day 1 are considered on-treatment for the following data domains: AEs, drug dispensation, exposure.

6.2 Treatment Regimens

The treatment group “as randomized” corresponds to the treatment group assigned by an Interactive Response Technology (IRT) system:

On Day 1, each subject will receive a single dose of nivolumab 480 mg or a single dose of nivolumab 960 mg in a double-blinded fashion. The time of initiation of dosing will be called “0” hour.

Treatment group “as treated”: The treatment group “as treated” is defined as the study treatment actually received.

6.3 Populations for Analyses

All enrolled subjects: All subjects who have a signed informed consent form and are registered into the IRT.

All randomized subjects: All subjects who are randomized to any treatment group in the study.

All treated subjects: All subjects who receive at least one dose of study drug.

The pharmacokinetic data set includes all available concentration-time data from subjects who receive BMS-936558.

The pharmacodynamic data set includes all available data from subjects for whom pharmacodynamic measurements are available at baseline and at least one other time point.

The immunogenicity data set consists of all available immunogenicity data from subjects who receive BMS-936558 and have at least 1 post treatment immunogenicity measurement.

Analyses of safety and extent of exposure will be based on all treated subjects. The study conduct and study population will be based on all randomized subjects.

Subjects are grouped by arm “as randomized” for demography, baseline disease characteristics and by arm “as treated” for disposition, extent of exposure and safety.

7 STATISTICAL ANALYSES

7.1 General Methods

Continuous variables will be summarized using descriptive statistics, eg, medians, minimums, maximums, and means with standard deviations/standard errors of the mean. Categorical variables will be summarized by frequencies and percentages. Percentages will be rounded and may not always add up to 100%.

Summaries are presented by treatment unless mentioned otherwise. Also, in all statistical analysis or summary statistics described in this section, missing values due to death will be considered as missing values unless mentioned otherwise.

7.2 Study Conduct

Relevant protocol deviations are summarized by treatment and total for treated subjects. Relevant protocol deviations are those that are programmable and could potentially affect the interpretability of the study results, such as:¹

- Certain inclusion or exclusion criteria;
- Incorrect dosing or study treatment assignment;

- Use of prohibited concomitant medications;
- Subjects remaining on treatment/in the study despite having met specified criteria for withdrawal.

A subject is considered to have a deviation of an inclusion or exclusion criterion only if all pre-treatment measurements fail the criterion. The consent date defines the beginning of enrollment. [Appendix 1](#) describes the relevant protocol deviations that can be programmed from the database.

7.3 Study Population

7.3.1 Disposition of Subjects

Summaries are presented by treatment and total as described in [Section 6.3](#), unless otherwise specified.

7.3.1.1 Pre-Treatment Subject Status and Accrual

Pre-treatment subject status is summarized for enrolled subjects. This presents the number of subjects enrolled, randomized, not randomized, treated and not treated. Reasons for not being randomized and not being treated are also included (e.g., AE, death, lost to follow-up).

Enrollment by country (as applicable) and investigative site is summarized for enrolled subjects and randomized subjects.

7.3.1.2 End of Treatment Subject Status

End of treatment subject status is summarized by treatment and total for treated subjects. This presents the number of subjects treated, completed the treatment period, did not complete the treatment period, reasons for not completing the treatment period (e.g. lack of efficacy, AE, death, lost to follow-up).

7.4 Demographics

Summaries are presented by treatment and total as described in [Section 6.3](#), unless otherwise specified.

7.4.1 Demographics

- Age
- Age characterization (<65, ≥65)
- Gender (Male, Female)
- Race (White, Black or African American, Asian, American Indian or Alaska Native, Native Hawaiian or Other Pacific Islander, Other)
- Ethnicity, for US only (Hispanic vs. Not Hispanic)
- Body weight
- Height
- Body Mass Index (BMI)

7.4.2 Baseline Characteristics

- Absolute lymphocyte count;
- Site of infection;
- Number of organ dysfunctions (0, 1, 2, 3, Organ dysfunctions: Hypotension, Acute respiratory failure, Acute kidney injury);
- Sequential Organ Failure Assessment (SOFA) score (continuous, total score and by category: Cardiovascular: 0-1 vs. 2-4; Respiratory: 0-1 vs. 2-4; Central Nervous System: 0-1 vs. 2-4; Renal: 0-1 vs. 2-4; Coagulation: 0-1 vs. 2-4; Liver: 0-1 vs. 2-4).

7.5 Extent of Exposure

7.5.1 Study Therapy

Dose Compliance

Subjects are considered dose compliant to study drug at the 95 level if dose infused is $\geq 95\%$ of target dose. Number of subjects compliant to dose is summarized applying 95, 75 and 50 and < 50 cutoffs.

7.5.2 Concomitant Medications

Concomitant medications, as recorded on the “Previous and Concomitant Medications” CRF, are summarized by arm. Prior medications are medications other than those in the study therapy that are taken during the index hospitalization within 1 week before the 1st day on treatment period. Concomitant medications are medications other than those in the study therapy that are taken on or after the first day on treatment period. Medications are presented alphabetically by anatomic class, therapeutic class and generic name using the WHO dictionary.

The use of immune modulating concomitant medication will also be summarized.

7.6 Efficacy

7.6.1 Exploratory Efficacy

Summary statistics will be provided for the following assessments by treatment and periodic time points. Listings will also be provided.

- Duration of mechanical ventilation, vasopressor use, or dialysis use separately during the index hospitalization.
- Sequential organ failure assessment (SOFA) scores at baseline and post-dosing time points, and change from baseline of SOFA scores during the index hospitalization.
- Length of ICU and hospital stay during index hospitalization.

7.7 Safety

Safety endpoints are assessed by treatment and total, unless otherwise specified.

All recorded AEs will be listed and tabulated by system organ class, preferred term, treatment and total. Summaries of AEs will include AEs, AEs by intensity, and AEs by relationship.

The investigators determine the intensity (graded according to National Cancer Institute Common Terminology Criteria for Adverse Events [CTCAE] Version 4.03.) of AEs and the relationship of AEs to study therapy. The investigators' terms are coded and grouped by system organ class using the latest version of the Medical Dictionary for Regulatory Activities (MedDRA) in production at BMS.

AEs are presented by system organ class and preferred term, each in descending order of frequency, unless otherwise specified.

Summaries of AEs include both SAEs and non-serious, unless otherwise specified. If a subject had an AE with different intensities during the study period, then only the worst grade is reported for a study period, unless otherwise specified.

Laboratory toxicities will be graded according to National Cancer Institute Common Terminology Criteria for Adverse Events (CTCAE) Version 4.03. The laboratory value during the study period with the worst grade will be reported for each test.

7.7.1 *Death*

All reported deaths after a subject is enrolled (i.e., has signed the informed consent) will be listed by subject. All-cause mortality and primary cause of death will be tabulated by treatment group and total.

7.7.2 *Serious Adverse Events*

SAEs are summarized by system organ class and preferred term, by treatment and total for on treatment period. The standard layouts are used:

- SAEs on-treatment
- Drug-related SAEs on-treatment

A listing of all SAEs, regardless of study period, is provided based on all treated subjects.

Two types of summaries are produced, one for subjects with grade 1-5 SAEs and a second restricted to subjects with grade 3-4 & grade 5 SAEs.

7.7.3 *Adverse Events Leading to Discontinuation*

AEs that lead to discontinuation during the on-treatment period are summarized by system organ class and preferred term. This analysis is presented by treatment and total for the on treatment period regardless of onset.

7.7.4 *Overall Adverse Events*

AE are summarized by descending frequency of SOC and preferred term within SOC. The tables will follow the standard layouts.

The following AE summaries will be produced:

- Adverse events on-treatment
- Drug-related adverse events on-treatment
- Adverse events on-treatment occurring in $\geq 5\%$ of subjects*
- Drug-related adverse events on-treatment occurring in $\geq 5\%$ of subjects*

* The 5% criterion cutoff refers to 5% in any column.

Two types of summaries are produced, one for subjects with grade 1-5 AEs and a second restricted to subjects with grade 3-4 & grade 5 AEs.

7.7.5 *Immune-Mediated Adverse Events*

In order to further characterize AEs of special clinical interest, an analysis of immune-mediated AEs (IMAEs) will be conducted. Immune-mediated AEs are specific events (or groups of PTs describing specific events) that include pneumonitis, diarrhea/colitis, hepatitis, nephritis/renal dysfunction, rash, endocrine (adrenal insufficiency, hypothyroidism/thyroiditis, hyperthyroidism, diabetes mellitus, and hypophysitis), and other specific events, considered potential immune-mediated events by investigator, that meet the definition summarized below:

- those occurring within 90 days of the dose,
- regardless of causality,
- treated with immune-modulating medication (of note, endocrine Adverse events such as adrenal insufficiency, hypothyroidism/thyroiditis, hyperthyroidism, diabetes mellitus, and hypophysitis are considered IMAEs regardless of immune-modulating medication use, since endocrine drug reactions are often managed without immune-modulating medication).

For the most recent immune-oncology studies, the data collection for IMAE was modified to also collect data on investigator assessment of potential IMAE including evidence of immune mediated etiology. For these studies, an additional criteria accounting for immune mediated etiology or immune mediated component is also to be considered:

- with no clear alternate etiology based on investigator assessment, or with an immune-mediated component

The list of MedDRA preferred terms used to identify Immune-Mediated adverse events is revisited quarterly and updated accordingly. The preferred terms used for the selection at the time of the database lock by categories will be provided.

IMAEs will be summarized by treatment group for each immune mediated category / PT using the 90-day safety window:

- Overall summary of AEs (subjects with grade 1-5 AEs) presented by immune mediate Category / PT. This summary includes all AEs that are qualified for IMAE preferred terms list, without requirement of either usage of immune modulating medications or accounting for immune mediated etiology or immune mediated component.

- Overall summaries of IMAEs [(subjects with grade 1-5 AEs) and (restricted to subjects with grade 3-4 & grade 5 AEs)] where immune modulating medication was initiated presented by Category / PT.
- Overall summaries of endocrine IMAEs [(subject with grade 1-5 AEs) and (restricted to subjects with grade 3-4 & grade 5 AEs)] presented by Category / PT.

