### Objectives and Endpoints:

Objective	Endpoint
Primary	

 
To assess the safety and tolerability of a single dose of nivolumab 480 mg or 960 mg in participants with severe sepsis or septic shock
 
To assess the pharmacokinetics of BMS-936558 in participants with severe sepsis or septic shock
 
	
 
Incidence rates of SAEs, AEs, immune-mediated AEs, AEs leading to discontinuation, deaths, and vital signs, ECG, or clinical laboratory abnormalities.
 
<math>C_{max}</math>, <math>C_{min}</math>, <math>C_{avg}</math>, <math>T_{max}</math>, <math>AUC(0-T)</math>, <math>CLT</math>, <math>V_d</math>, <math>T_{1/2}</math>.
 

Secondary	

 
To assess receptor occupancy of nivolumab following single dose administration
 
To assess the effect of a single dose of nivolumab on monocyte HLA-DR expression and absolute lymphocyte count
 
To assess the immunogenicity of nivolumab following single dose administration
 
	
 
Receptor occupancy on T cells at baseline and after study treatment administration at planned sampling time points
 
Baseline and post-dosing assessments of mHLA-DR expression on monocytes, of absolute lymphocyte count
 
Number and percentage of participants with detectable anti-nivolumab antibodies at baseline and following single dose administration of nivolumab and the relationship with other outcome measures
 

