**Contacts for SAE reporting are specified in Appendix 3.**

### **9.2.1 Immune-mediated Adverse Events**

Immune-mediated AEs are AEs consistent with an immune-mediated mechanism or immune-mediated component for which non-inflammatory etiologies (e.g. infection or tumor progression) have been ruled out. Immune-mediated AEs can include events with an alternate etiology which were exacerbated by the induction of autoimmunity. Information supporting the assessment will be collected on the subject's case report form.

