### **9.2.2 Time Period and Frequency for Collecting AE and SAE Information**

The collection of nonserious AE information should begin at initiation of study treatment at the time points specified in the Schedule of Activities ([Section 2](#)) and for a minimum of 90 days following discontinuation of study treatment. Every adverse event must be assessed by the investigator with regard to whether it is considered immune-mediated. For events which are potentially immune-mediated, additional information will be collected on the participant's case report form. Nonserious AE information should also be collected from the start of a placebo lead-in period or other observational period intended to establish a baseline status for the participants.

Sections 5.6.1 and 5.6.2 in the Investigator Brochure (IB) represent the Reference Safety Information to determine expectedness of serious adverse events for expedited reporting. Following the participant's written consent to participate in the study, all SAEs, whether related or not related to study drug, must be collected, including those thought to be associated with protocol-specified procedures.

All SAEs must be collected that occur during the screening period and within 90 days of discontinuation of dosing.

- Medical occurrences that begin before the start of study treatment but after obtaining informed consent will be recorded on the appropriate section of the eCRF section.
- All SAEs will be recorded and reported to Sponsor or designee within 24 hours, as indicated in [Appendix 3](#).
- The investigator will submit any updated SAE data to the sponsor within 24 hours of this being available.

Investigators are not obligated to actively seek AEs or SAEs in former study participants. However, if the investigator learns of any SAE, including a death, at any time after a participant has been discharged from the study, and he/she considers the event reasonably related to the study treatment or study participation, the investigator must promptly notify the sponsor.

The method of evaluating, and assessing causality of AEs and SAEs and the procedures for completing and reporting/transmitting SAE reports are provided in [Appendix 3](#).

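### SAP 7.7.5 plans no table of immune-mediated AE incidence, a primary safety endpoint, on the Protocol 9.2.1 definition

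*SAP*

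**What the plan says.** The Protocol Synopsis lists as a primary endpoint "Incidence rates of SAEs, AEs, immune-mediated AEs, AEs leading to discontinuation, deaths". SAP 4.1 repeats it: the safety objective "will be measured by the incidence rates of AEs, SAEs, AEs leading to discontinuation, immune-mediated AEs, and deaths".

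Protocol 9.2.1 defines an immune-mediated AE as one consistent with an immune mechanism or component "for which non-inflammatory etiologies (e.g. infection or tumor progression) have been ruled out". It then widens the definition: "Immune-mediated AEs can include events with an alternate etiology which were exacerbated by the induction of autoimmunity". It mentions neither treatment of the event nor a list of preferred terms. Protocol 9.2.2 supplies the data: "Every adverse event must be assessed by the investigator with regard to whether it is considered immune-mediated".

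SAP 7.7.5 works from named event categories and the preferred terms in Appendix 2. It requires onset within 90 days of the dose, disregards causality, and sets a treatment criterion: "treated with immune-modulating medication (of note, endocrine Adverse events such as adrenal insufficiency", with the parenthesis exempting endocrine events. Events outside the named categories can enter on investigator judgement, but only as "other specific events, considered potential immune-mediated events by investigator, that meet the definition summarized below". A further criterion on etiology is introduced for recent immune-oncology studies, in addition to the treatment criterion.

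The section then plans three summaries: (1) all AEs with a listed term, waiving both the medication and the etiology criteria; (2) IMAEs for which an immune-modulating drug was started; (3) endocrine IMAEs.

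**The concern.** The protocol names an endpoint and defines it; the SAP carries the same name but counts something else. On etiology the two largely agree, because the SAP also admits events with an immune-mediated component. They differ on two other points: the SAP requires treatment for every non-endocrine event, and it selects through a term list. Whether an event is treated depends on its severity and on local practice, which is a different question from whether its mechanism is immune.

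If the SAP is followed exactly, the study report will carry counts labelled as immune-mediated AEs, and no planned table will state the rate that the protocol defined as primary.

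**Working it through.** **Step 1. Trace each kind of event through the plan.** For AEs within 90 days of the dose, reading Protocol 9.2.1 against the three summaries in SAP 7.7.5:

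| Event | Protocol 9.2.1 | Summary 1 (listed terms) | Summary 2 (drug started) | Summary 3 (endocrine) |
|---|---|---|---|---|
| Immune-mediated, endocrine, listed | counts | in, unflagged | only if treated | in |
| Immune-mediated, non-endocrine, listed, treated | counts | in, unflagged | in | out |
| Immune-mediated, non-endocrine, listed, untreated | counts | in, unflagged | **out** | **out** |
| Immune-mediated, non-endocrine, unlisted, untreated | counts | **out** | **out** | **out** |
| Other cause, non-endocrine, listed, untreated | does not count | **in** | out | out |

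No column reproduces the protocol's column.

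- Summary 1 is too broad, since listed terms such as acute kidney injury, diarrhoea and raised bilirubin count whatever their cause. Acute kidney injury is itself one of the qualifying organ dysfunctions in Protocol 6.1. The summary is also too narrow, since unlisted terms never enter.
- Summaries 2 and 3 omit the untreated non-endocrine event. They are also separate and can overlap, so they do not add up to one incidence.
- The route for other events on investigator judgement does not help, because those events must still meet the treatment criterion.

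**Step 2. Check the other AE tables.** SAP 7.7.2 to 7.7.4 select on seriousness, drug relationship, discontinuation, grade or frequency. None selects on the investigator's immune-mediated assessment.

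**Step 3. Size.** The documents give no immune-mediated AE rate in sepsis, so what follows is illustration.

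- The plan's own figure: with 15 per arm and 10% incidence (SAP 5), P(at least one) = 1 − 0.9^15 = 0.794, which agrees with the stated 80%.
- Suppose the incidence on the protocol's definition is 10%, and a share f of affected participants have only untreated non-endocrine events (f is assumed). The incidence on the SAP's definition is then 10% × (1 − f), and P(at least one counted in 15) = 1 − [1 − 0.10(1 − f)]^15:

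| f | Incidence on SAP definition | P(at least one in 15) |
|---|---|---|
| 0 | 10% | 79% |
| 0.25 | 7.5% | 69% |
| 0.50 | 5% | 54% |
| 0.75 | 2.5% | 32% |

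- One omitted participant in 15 is 1/15 = 6.7 points. Exact (Clopper-Pearson) 95% limits: 0/15 gives 0 to 21.8% (upper limit 1 − 0.025^(1/15)); 1/15 gives 0.2 to 31.9%.
- Fifteen is a ceiling. If an arm held only 6 treated participants (an assumed floor, borrowed from the PK-profile target), one is 1/6 = 16.7 points: 0/6 gives 0 to 45.9%, and 1/6 gives 0.4 to 64.1%.

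**Step 4. A separate mismatch.** Protocol 10.3.1 plans a tabulation of immune-related AEs that includes a breakdown by time point. SAP 7.7.5 plans only category and preferred-term summaries over the whole 90-day window, and does not say that the breakdown is dropped.

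**The case against.** The best defence is that nothing is lost. Every recorded AE is listed and tabulated under SAP 7.7. For listed terms, summary 1 gives an inclusive count and summaries 2 and 3 give restrictive ones. The term list is revisited quarterly, so the gap for unlisted terms may narrow. An SAP may also turn a judgement-based definition into programmable criteria, and here the judgement is hard: every participant has documented or suspected infection, which is one of the causes to be ruled out. Nothing in the plan tests a hypothesis on this endpoint.

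Much of this is true, and it limits the consequence. It does not supply the missing number. An event that is present but unflagged among all AEs does not give an incidence for a named primary endpoint, and updating the term list leaves the treatment criterion in place. Operational criteria are legitimate, but the SAP neither says that it departs from Protocol 9.2.1 nor explains why.

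Two limits on the illustrations also stand. The six-per-arm figure is a PK target, whereas safety uses all treated participants, so an arm that small is unlikely. And although Appendix 2 as printed has no amylase, lipase or pancreatitis term while both enzymes are study laboratory tests, the documents do not name such events as immune-mediated effects of nivolumab. That example shows only what happens to an unlisted term.

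**Conclusion.** The concern holds. Followed as written, the SAP never produces the incidence of immune-mediated AEs as Protocol 9.2.1 defines them, and untreated non-endocrine events judged immune-mediated are outside its IMAE definition. This follows from the wording alone and holds whether or not the etiology criterion, phrased for immune-oncology studies, is taken to apply to this sepsis trial, because that criterion adds to the treatment requirement and does not replace it.

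The number of participants affected cannot be derived from the documents. The shares in the working are assumptions, and the true number may be zero. With at most about 15 per arm, though, a single participant visibly changes the reported rate. The effect is on what is reported for a primary endpoint, with no bearing on a test or decision threshold. It should be fixed, and confidence in its practical importance is moderate.

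**What to change.** In SAP 7.7.5:

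- Add a primary table of IMAE incidence, by treatment and total. It should count participants with at least one AE within 90 days of the dose that the investigator assessed as immune-mediated under Protocol 9.2.1, including events with an immune-mediated component, regardless of term list or medication.
- Keep the three existing summaries and label them supportive.
- Add the time-point breakdown from Protocol 10.3.1, or state that it is dropped.
- As a clarification, replace the immune-oncology wording with a statement that the etiology criterion applies to CA209923.

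The cost is SAP wording and one table, plus the time split if it is kept. No new data are needed, since Protocol 9.2.2 already requires the assessment for every AE. The drawback is that the count depends on investigator judgement in infected patients and may be too low; the supportive summary of all listed terms shows the broader count beside it.
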